Based on the original trial design in the previous trial, the estimated time to progression was 7.6 months ((64)). This includes both PSA progression and new metastatic lesions. Additionally, this included a proportion of patients who had not progressed on previous anti-androgens. Overall there is great variability reported in the literature for time to progression with D0.5 prostate cancer and there is no clear data on time to PSA-progression in this population (D0.5 Prostate Cancer). A large study followed over 3000 prostate cancer patients in the PSA era from Johns Hopkins. The data from 91 patients who eventually developed metastatic disease suggested that time from D0.5 disease to metastasis was only 8 months in patients treated with primarily with radical prostatectomy. ((66)). This is consistent with the previous study here that

demonstrated a median time to progression of 7.6 months, which included PSA progression. This time to progression (7.6 months) also served as the statistical basis for this study.

1.2.7 Rationale for treating patients previously treated with flutamide in the (neo)adjuvant setting.

Many patients have been previously treated with flutamide, but still should be considered for re-treatment with flutamide and thus should be considered for this protocol. Some patients may have been treated with this agent previously as part of a neoadjuvant or adjuvant hormonal treatment for patients undergoing primary radiation therapy. For some patients, flutamide is administered for up to 6-8 weeks in an effort to prevent a “flare” after initial GnRH agonist. Others may have discontinued flutamide as part of an intermittent treatment approach. From a clinical stand point, if the patient has not had a rising PSA on previous flutamide, they could be re-treated with this agent with reasonable expectation of response. ((67)) Therefore, eligible patients may have been treated with previous flutamide as long as the patient did not have a rising PSA while on flutamide. Patients will be required to be at least 1 year removed from previous flutamide exposure.

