- K. No known brain metastasis, or with a history of seizures, encephalitis, or multiple sclerosis.
- L. Patients with a serious hypersensitivity reaction to egg products are not eligible.
- M. Prior splenectomy.
- N. Patients who have received prior flutamide therapy in the last year. (Patients treated with flutamide in the neoadjuvant or adjuvant setting or those previously treated with flutamide who did not have a rising PSA on treatment would be allowed to enroll on the protocol.)

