3 STUDY IMPLEMENTATION

3.1 Study Design (see Schema)

This randomized Phase II study proposes to evaluate the role of second line antiandrogen therapy and a pox vector based PSA vaccine in a population of patients with prostate cancer who have a rising serum PSA despite castrate levels of testosterone and prior antiandrogen therapy but no metastatic disease on bone or CT scans. Patients will be randomized on a 1:1 basis to Arm A (flutamide alone) or Arm B (flutamide + vaccine).

Arm A: Flutamide 250 mg orally TID beginning on day 1.

Arm B: Flutamide 250 mg orally TID beginning on day 1.

PROSTVAC-V/TRICOM (vaccinia) 2×10^8 pfu subcutaneously on day 1 of the first cycle only, followed by monthly (every 4 week) boosting vaccinations with PROSTVAC-F/TRICOM (fowlpox) 1×10^9 pfu subcutaneously on day 1 of each cycle. The duration of each treatment cycle is approximately 28 days.

[figure not shown]
Patients may continue on the therapy they were randomized to until the development of measurable disease on scans, rising serum PSA, or if they develop toxicity requiring stopping of their treatment. For patients with declining PSA no restaging will be done unless they develop symptoms consistent with metastatic disease. For patients with rising PSA, once 2 consecutive

PSA rises are seen from the last imaging studies, CT and bone scans will be done at their next scheduled visit. They will then be re-staged (CT and bone scans) at 3 month intervals as long as PSA continues to rise.

1. Patients on either arm who develop clinical progression (i.e. evidence of metastatic disease on scans) will be taken off study.
2. Patients who do not develop clinical progression (as defined above), but develop biochemical recurrence (i.e rising serum PSA levels) will undergo the following:
 - After 3 months of therapy, patients randomized to the flutamide alone (arm A) may cross over to receive vaccine if they develop a rising PSA and scans are without metastatic disease. The vaccine may commence 4 weeks after flutamide is stopped (if the PSA continues to rise. If there is an antiandrogen withdrawal response (a decline in PSA 28 days after the discontinuation of flutamide), PSA serum levels will be checked every 28 days and vaccine may commence when the serum PSA levels begin to rise (if scans are negative for metastasis and if patients continue to meet the eligibility criteria as outlined in section 2.1).

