5.2 Response Criteria

- 5.2.1 Methods of Measuring Disease Progression (note: patient's must have non-metastatic disease as an eligibility criteria-see [2.1.1 B Inclusion Criteria](#). New lesions by RECIST Criteria will be for definition of disease progression. Rising serum PSA levels will also be used for determining disease progression-see [5.2.1.3](#) and [5.2.2](#))

All patients in this study must be assessed for response to treatment, even if there are major treatment deviations. Each patient will be assigned one of the following categories: 1) complete response; 2) partial response; 3) stable disease; 4) progressive disease; and 5) not evaluable (early death from malignant disease, early death from toxicity, early death due to other causes, or unknown-not assessable, insufficient data). This protocol will use CTEP's Response Evaluation Criteria on Solid Tumors (RECIST) for assessing response. A quick reference to the RECIST guidelines can be downloaded at the following URL: <http://ctep.cancer.gov/guide>. A copy of this quick reference is found in D.

For patients with declining PSA no restaging will be done unless they develop symptoms consistent with metastatic disease. For patients with rising PSA, once 2 consecutive PSA rises are seen from the last imaging studies, CT and bone scans will be done at their next scheduled visit. (Therefore, restaging scans would be done at an interval no less than 3 months.) They will then be re-staged (CT and bone scans) at 3 month intervals as long as PSA continues to rise.

1. Patients on either arm who develop clinical progression (i.e. evidence of metastatic disease on scans) will be taken off study.
2. Patients who do not develop clinical progression (as defined above), but develop biochemical recurrence (i.e rising serum PSA levels) will undergo the following:
 - Patients randomized to Arm A will have flutamide discontinued and may begin to receive the vaccine as described above following a 4 week delay to determine if there is evidence of an antiandrogen withdrawal response (if they continue to meet the eligibility criteria as outlined in section [2.1](#))
 - Patients randomized to Arm B will have flutamide discontinued, but may continue to receive vaccine treatment.

3. If patients continue to develop biochemical progression following the maneuvers outlined in #2 above, they will come off-treatment, but can remain on study until the development of metastatic disease on scans.

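### Exclusion N in 2.1.2 does not carry over both conditions that 1.2.7 sets for men with earlier flutamide, so it can admit men whom 1.2.7 bars.

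*Combined protocol and SAP*

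**What the plan says.** Two places in the protocol deal with flutamide taken before the trial.

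- **Section 1.2.7 (rationale).** Of the men it covers, it says "Some patients may have been treated with this agent previously as part of a neoadjuvant or adjuvant hormonal treatment". It also mentions short courses given to prevent flare and intermittent treatment. It then sets two conditions: "eligible patients may have been treated with previous flutamide as long as the patient did not have a rising PSA while on flutamide", and "Patients will be required to be at least 1 year removed from previous flutamide exposure". Neither carries an exception.
- **Section 2.1.2, exclusion N (operative rule).** The main sentence excludes "Patients who have received prior flutamide therapy in the last year". A bracket follows. It names men treated in the neoadjuvant or adjuvant setting and then adds that "those previously treated with flutamide who did not have a rising PSA on treatment would be allowed to enroll on the protocol".

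Inclusion B in 2.1.1 sets withdrawal periods for nilutamide (4 weeks) and bicalutamide (6 weeks), but none for flutamide. N is therefore the only item in 2.1 that deals with flutamide exposure.

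**The concern.** Sites enrol against section 2.1 and the checklist, not against the rationale. If N says less than 1.2.7, or says it ambiguously, two careful readers can reach different decisions on the same man.

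Three things are at stake.

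- **Patients.** Both arms receive flutamide. A man admitted after a PSA rise on flutamide is given again a drug that has already failed him. By 1.2.7's own argument, a reasonable expectation of response rests on there having been no such rise.
- **Signal.** If such men tend to fail early whatever their arm (an assumption, since the documents give no figure), they dilute any difference in time to treatment failure.
- **Analysis set.** Sections 5.2.4.2 and 5.2.4.3 base the main response analysis, and all conclusions, on eligible patients. If eligibility has two readings, so does that set.

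**Working it through.** This is a comparison of rules. The only arithmetic is a check that the sample size is not involved.

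**Step 1. The plan's own figure.** Section 5.4, after Amendment F, plans 31 men per arm for medians of 10.0 and 18.0 months, one-tailed alpha 0.1 and 80% power, with accrual A = 60 months and further follow-up F = 24 months. With exponential hazards h of 0.0693 and 0.0385 per month and uniform accrual:

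P(event) = 1 − [exp(−hF) − exp(−h(A+F))]/(hA)

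This gives 0.955 and 0.845, so about 31 × (0.955 + 0.845) = 55.8 events. Power is 0.820 by Schoenfeld's formula and 0.801 by Lachin–Foulkes. The figure reproduces, and none of its inputs depends on the wording of N.

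**Step 2. The two rules side by side.** 1.2.7 uses two yes/no facts: how long ago flutamide was taken, and whether PSA rose on it. That makes four kinds of man.

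| Earlier flutamide | 1.2.7 | N, main sentence alone | N, bracket read as an exemption |
|---|---|---|---|
| 1 year or more ago, no PSA rise | admit | admit | admit |
| 1 year or more ago, PSA rose | bar | not excluded | not excluded in terms; at most implied |
| Within 1 year, no PSA rise | bar | bar | admit |
| Within 1 year, PSA rose | bar | bar | bar, except perhaps a (neo)adjuvant user |

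1.2.7 admits one row of four. N's main sentence leaves two rows open. With the bracket read as an exemption, three are open. The last row is uncertain because the bracket lists (neo)adjuvant users as a separate group, and it is unclear whether the no-PSA-rise condition applies to them.

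**Step 3. Two concrete men.**

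- *PSA rose on flutamide two years ago.* 1.2.7 bars him. N's main sentence does not reach him, since his exposure is older than a year. The bracket says who may enrol and leaves his exclusion to inference.
- *Adjuvant flutamide six months ago, no PSA rise.* 1.2.7 bars him on the interval. N's main sentence also bars him, but the bracket then appears to let him in on both of its limbs.

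**Step 4. Does another item close the gap?** No. Inclusion B requires a rising PSA at castrate testosterone, with withdrawal rules for the other two antiandrogens only. Nothing else in 2.1.1 or 2.1.2 mentions flutamide.

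**Step 5. Size.** The documents give no count of men with earlier flutamide, no split by interval and no PSA history on it. No number affected and no loss of power can be derived, and none is claimed.

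**The case against.** The best defence is that N and 1.2.7 can be read in harmony. N's main sentence agrees with the one-year rule. The bracket can be taken as a clarification about older exposure, acceptable if PSA did not rise. Permitting men without a PSA rise would be pointless if men with one were also permitted. 1.2.7 states the intent in mandatory terms in the same protocol. Section 2.3 requires a checklist, central registration and a route for eligibility questions, and 5.5 adds eligibility review by the coordinating centre.

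Much of this stands. The intent is clear and the practical effect is probably small. But the harmonious reading needs the reader to bring in from 1.2.7 what N leaves out: the PSA-rise exclusion, and the fact that the interval applies in every setting. Central review helps only if the reviewer applies 1.2.7 and not N as worded.

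A reader might go further and infer that N blocks the Arm A crossover. Section 5.2.1 lets these men start vaccine "if they continue to meet the eligibility criteria as outlined in section" 2.1. For men with a withdrawal response, 3.1 adds "if patients continue to meet the eligibility criteria as outlined in section 2.1". Each has just taken flutamide. The documents do not support that inference:

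- N speaks of prior therapy and of who may enrol, which naturally means exposure before enrolment.
- 5.2.1 puts the re-check in the same sentence that stops flutamide and starts vaccine after four weeks.
- Under 3.1, Arm A men "may cross over to receive vaccine if they develop a rising PSA and scans are without metastatic disease", so a PSA rise on flutamide is the route into crossover. Counting on-study flutamide under N would cancel the provision for nearly every man it covers.
- 5.4 also plans for Arm A men to go on to vaccine.

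Nothing suggests that a crossover would be refused or delayed.

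**Conclusion.** The mismatch is real and minor. N omits one of 1.2.7's two conditions and, through its bracket, makes the other doubtful. As written it can admit men whom the rationale says are barred. How many is unknown.

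A reader might infer a biased comparison or a quantifiable loss of power. Neither follows. Randomisation puts such men in both arms, so the effect on the comparison is dilution, along with re-treatment that 1.2.7 meant to avoid. The planned 62, the alpha level and the primary comparison are unchanged.

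The conclusion rests on two assumptions: that section 2.1, not the rationale, governs enrolment, and that the eligibility checklist, which is not reproduced in the document, follows N.

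**What to change.** Delete N and its bracket and replace them with two exclusions:

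1. Any flutamide within 1 year before enrolment, whatever the setting in which it was given.
2. A rise in PSA while taking flutamide at any time before enrolment.

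Align the eligibility checklist if it mirrors the current N. The words *before enrolment* also make plain that flutamide taken on study does not count when section 2.1 is re-checked at the Arm A crossover. That is tidying, not correction of an error.

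The cost is two sentences in 2.1.2 and perhaps a checklist line. There may be a few fewer eligible men. The number is unknown, and it matters somewhat because accrual was slow: 5.4 reports 13 men in about two years at Amendment F, with 62 − 13 = 49 still to enrol in three. No change to the analysis or the sample size is needed.

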2.2 Research Eligibility Evaluation

- A. The following tests may be obtained anytime prior to enrollment:
1. Pathological confirmation of diagnosis and PSA expression in the Laboratory of Pathology at NIH Clinical Center or participating institute's Department of Pathology prior to starting this study will be required. However, if no pathologic specimen is available, patients may enroll with a pathologist's report showing a histologic diagnosis of prostate cancer and a clinical course consistent with the disease.
- B. The following parameters will be obtained within 8 weeks prior to start of enrollment:
1. HIV test
 2. Hepatitis B and C
- C. The following parameters will be obtained within 28 days prior to start of enrollment:
1. Tc-99 whole body scintigraphy
 2. CT of chest/abdomen /pelvis
 3. Baseline electrocardiogram (EKG) on all patients, and appropriate cardiologic evaluation, as clinically indicated, to provide baseline function and identify any patients who should be monitored closely for cardiac risks associated with vaccinia vaccination
- D. The following parameters will be obtained within 16 days prior to start of treatment:
1. Clinical Evaluation
 - History and physical examination
 - ECOG performance status (see **APPENDIX A**)
 - Height, Weight
 2. Laboratory studies
 - Complete blood count plus differential and platelet count
 - Acute care panel (electrolytes, BUN, creatinine)
 - Liver panel (AST/ALT/total bilirubin)
 - Alkaline phosphatase, LDH
 - Urinalysis, 24 hour urine collection to evaluate creatinine clearance, proteinuria, and urine electrolytes
 - ANA
 - Serum PSA and PAP
 - Lymphocyte phenotyping CD4/CD8 (This will be performed for patients enrolled at the NCI site only)

2.3 Patient Registration and Treatment Randomization

All patients must have completed an eligibility checklist. Projected PSA doubling time is a stratification factor in the randomization (see formula in Section 5.4). Patients must be registered with Central Registration Information Services within 24 hours of signing the consent. Authorized staff must register patients by faxing the eligibility checklist from the web site (<http://home.ccr.cancer.gov/intra/eligibility/welcome.htm>) to the Central Registration Office at [contact].

For randomization, authorized staff should call [contact] between the hours of 8:30 a.m. and 5:00 p.m., Monday through Friday. A recorder is available during non-working hours.

For Participating site Registration:

All patients must be registered through the NCI Central Registration Office (CRO). The CRO is open from 8:30am to 5:30pm EST Monday through Friday, excluding federal holidays. A protocol registration form and cover memo will be supplied by the Coordinating Center, NCI CCR and updates will be provided as needed. Subject eligibility and demographic information is required for registration. To register a subject, fax the completed registration checklist and cover memo to the CRO at [contact]. Please indicate on the protocol registration form whether the patient is screening or is eligible to start treatment. The CRO will notify you either by e-mail or fax that the protocol registration form has been received. The CRO will assign a unique patient/subject ID number for each subject that will be used to enter data into the C3D data base. Questions about eligibility should be directed to the Coordinating Center's Research Nurse, [name], [contact], [contact]. Technical questions about the form should be directed to the Central Registration Office [contact]).

A copy of the registration checklist form should be faxed to Coordinating Center Research Team at [contact].

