- For patients who have stable disease and attend clinic every 8 weeks, once 2 consecutive PSA rises are seen, a CT and bone scan will be done at their next visit in 4 weeks. They will then be restaged (CT and bone scans) at 3 month intervals as long as PSA continues to rise.

SCHEMA

This randomized Phase II study proposes to evaluate the role of second line antiandrogen therapy and a pox vector based PSA vaccine in a population of patients with prostate cancer who have a rising serum PSA despite castrate levels of testosterone and prior antiandrogen therapy but no metastatic disease on bone or CT scans. We will look for a potential clinical benefit using an initial vaccination with 2×10^8 pfu PROSTVAC-TRICOM -V on day 1 followed by monthly boosting vaccinations with 1×10^9 pfu PROSTVAC-TRICOM -F. The duration of each treatment cycle is approximately 28 days. In addition to the vaccine therapy, 2nd line antiandrogen therapy with flutamide will be given orally on a daily basis beginning with the first vaccine on day 1. This will be compared to patients receiving flutamide alone. Patients may continue on therapy until the development of measurable disease on scans or if they develop toxicity requiring stopping of their treatment. For patients with declining PSA no restaging will be done unless they develop symptoms consistent with metastatic disease. For patients with rising PSA, once 2 consecutive PSA rises are seen from the last imaging studies, CT and bone scans will be done at their next scheduled visit. They will then be re-staged (CT and bone scans) at 3 month intervals as long as PSA continues to rise. After the initial 3 month evaluation, if a patient has a rising serum PSA level (based on Bubley criteria JCO, 1999) but no evidence of metastatic disease, patients in Arm A will have flutamide discontinued and may begin to receive vaccine alone 4 weeks after cessation of flutamide (if there is no evidence of an antiandrogen withdrawal response) as described above, since the standard care would be discontinuation of flutamide for rising serum PSA. If there is an antiandrogen withdrawal response (a decline in PSA 28 days after the discontinuation of flutamide), PSA serum levels will be checked every 28 days and vaccine may commence when the serum PSA levels begin to rise (if scans are negative for metastasis). Those patients who have rising serum PSA levels on Arm B without evidence of metastatic disease will have flutamide discontinued, but may continue to receive vaccine treatment. Since there is no standard of care aside from antiandrogen discontinuation for these patients and they would have already received 2nd line therapy, patients can continue to receive treatment on study until there is evidence of disease on bone scan or CT scan or until there is a second occurrence of rising PSA levels in the absence of clinical progression. For patients who have been on study for 2 years or more with stable disease and who are not getting vaccine, clinic visits may be scheduled at 8 week intervals. For these patients who have rising PSA, once 2 consecutive PSA rises are seen, a CT and bone scan will be done at their next visit in 4 weeks. They will then be restaged (CT and bone scans) at 3 month intervals as long as PSA continues to rise. Patients will be stratified based on a “projected” PSA doubling time of >10 months vs. ≤ 10 months using last 2 serum PSA levels 1 month apart prior to enrolling on study.

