 - Patients randomized to Arm B will have flutamide discontinued, but may continue to receive vaccine treatment until the development of disease on scans or a second occurrence of rising PSA levels in the absence of clinical progression.
3. If patients continue to develop biochemical progression following the maneuvers outlined in #2 above, they will come off-treatment, but can remain on study until the development of metastatic disease on scans.

[figure not shown]
Arm A (n=33)

Flutamide

Arm B (n=33)

Vaccine (monthly) + Flutamide (daily)

Stratification of patients- projected PSA doubling time of >10 months vs ≤ 10 months (based upon last 2 serum PSA levels prior to enrollment 1 month apart)

At week 12, restaging CT Chest/Abdomen/Pelvis and Bone scans will be performed in all patients. For patients with declining PSA no restaging will be done unless they develop

symptoms consistent with metastatic disease. For patients with rising PSA, once 2 consecutive PSA rises are seen from the last imaging studies, CT and bone scans will be done at their next scheduled visit. They will then be re-staged (CT and bone scans) at 3 month intervals as long as PSA continues to rise. Patients may continue on therapy if scans do not demonstrate metastatic prostate cancer. For patients who have been on study for 2 years or more with stable disease and who are not getting vaccine, clinic visits may be scheduled at 8 week intervals. For these patients who have rising PSA, once 2 consecutive PSA rises are seen, a CT and bone scan will be done at their next visit in 4 weeks. They will then be restaged (CT and bone scans) at 3 month intervals as long as PSA continues to rise.

Legend

H = Flutamide 250 mg po t.i.d, commencing on day 1 in both arms

V= PROSTVAC-V /TRICOM 2×10^8 pfu s.c

F= PROSTVAC-F /TRICOM 1×10^9 pfu s.c

↓ Blood draw for Immunologic studies- a. Elispot assay (see section 3.4.6 and APPENDIX C).

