D0.5 prostate cancer) conducted at the NCI (protocol 00-C-0137) identified a 7.6 month median time to treatment failure, using the definition above. In the current trial, Flutamide will be used instead of Nilutamide because it has a potentially more favorable toxicity profile. The objective will be to determine, in the context of a randomized phase 2.5 trial, if the addition of vaccine to flutamide alone may be associated with an improvement in time to treatment failure.

The study will be randomized in a 1:1 fashion, and will enroll 33 eligible patients on each of the two arms (66 total), in order to have 80% power to detect a difference between a hypothesized median TTF of 7.6 months on flutamide alone and an increase of 6 months, to 13.6 months, with flutamide + vaccine, using a one-tailed 0.1 alpha level test. This calculation was made using nQuery Advisor version 5, assuming 36 months accrual, an additional 12 months of follow-up for the last patient enrolled, and hazards of 0.0912 per month for flutamide alone and 0.0510 for flutamide and vaccine, with a resulting hazard ratio of 1.788.

The ELISPOT assay will be performed in HLA-A2 patients. The log changes in precursor T cell frequency from pre-treatment to that after 3, 6, and 9 months of therapy will be determined and evaluated for statistical significance, both within an arm and between arms. Since this assay will only be available on a subset of patients, the power to detect differences is unknown and may be limited, and the results will be considered secondary, exploratory and possibly biased. The results will be carefully reported with necessary caveats. In addition, since there is no evidence at this time that HLA-A2 patients will have a significantly different time to treatment failure than those with other HLA types, this parameter will not be used to stratify the randomization.

Toxicity evaluations will take place during each cycle of therapy and worst grades of toxicity, by type, will be compared in a secondary analysis between the study arms.

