Early stopping Rule- Should 2 patients in the first 10 patients enrolled on both arms of the trial exhibit a grade 4 toxicity of any type, regardless of the number of patients enrolled (from 2 to 10), then the trial will be temporarily closed to accrual to reevaluate the use of the agents in this combination. The exact upper 90% confidence bound about 2/10 is 45%, while that about 1/10 is 34%. Thus, while 1/10 is marginally consistent with one third of the patients having toxicity, 2/10 is consistent with more than this amount; thus 2 patients with toxicity early in the study are more than would be tolerated in a phase II study of this type.

Those patients who experience a PSA progression while on their initial, randomized therapy will stop flutamide treatment when this is determined. If they were randomized to receive vaccine + flutamide, they will begin to receive vaccine (alone), and if randomized to flutamide alone, they will start vaccine alone instead. The time to development of metastatic disease from the date of discontinuation of flutamide will be evaluated as a secondary endpoint for each arm, using Kaplan-Meier curves. Descriptive analyses of the pattern of change in PSA over time will also be performed.

It is expected that approximately 20-25 patients per year may be enrolled onto this trial. Thus, in order to obtain 66 evaluable patients, accrual of approximately three years will be expected. In order to allow for a very small number of patients who are inevaluable early after enrollment, the accrual ceiling will be set at 70 patients.

Following amendment F, the study will be continue to be randomized in a 1:1 fashion, and will enroll 31 eligible patients on each of the two arms (62 total), in order to have 80% power to detect a difference between a hypothesized median TTF of 10.0 months on flutamide alone and an increase of 8 months, to 18.0 months, with flutamide + vaccine, using a one-tailed 0.1 alpha level test. This difference assumes that patients enrolled on the study will be equally divided between those who have progressed on combined androgen therapy as well as those who have just begun combined androgen therapy. This calculation was made using nQuery Advisor version 5, assuming 60 months accrual, an additional 24 months of follow-up for the last patient enrolled, and hazards of 0.0693 per month for flutamide alone and 0.0385 for flutamide and vaccine, with a resulting hazard ratio of 1.80.

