Following amendment F, patients will be stratified by combined androgen therapy status (progressed; beginning) as well as projected PSA doubling time (≤ 10 vs. > 10 months).

As of the date of Amendment F, 13 patients have enrolled onto the study in approximately 2 years. In order to accrue a total of 62 patients in 5 years, the remaining 49 patients would need to be accrued in 3 years, or approximately 16-18 patients per year. In order to allow for a small number of inevaluable patients, the accrual ceiling will be set at 65.

Following Amendment K, only the patients at NCI will receive sargramostim (GM-CSF). Given the relatively small amount of patients which remain on the trial, descriptive and exploratory analysis will be done comparing patients who received GM-CSF and those who did not.

Following Amendment P, patients at NCI will not receive sargramostim injections. There has not been found to be definitive benefit of the Sargramostim injections to this point. Other studies using the RF-PSA TRICOM are not currently using Sargramostim injections; and the subjects in the multicenter sites are also not required to take/give Sargramostim.

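### Sections 2.3, 3.1 and the Schema still stratify on PSA doubling time alone, and 3.1 shows 33 per arm, although section 5.4 after Amendment F requires a second factor and 31 per arm

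*Combined protocol and SAP*

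**What the plan says.** **Randomisation.** Section 2.3 states: "Projected PSA doubling time is a stratification factor in the randomization (see formula in Section 5.4". Its pointer to 5.4 is for the doubling-time formula. No second factor is named.

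**Design.** Section 3.1 reads: "Stratification of patients- projected PSA doubling time of >10 months vs ≤ 10 months". It labels Arm A and Arm B n=33 each. The Schema says: "Patients will be stratified based on a “projected” PSA doubling time of >10 months vs. ≤ 10 months". Both describe patients with "rising serum PSA despite castrate levels of testosterone and prior antiandrogen therapy".

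**Statistics before Amendment F.** Section 5.4 first gives the design under which the trial "will enroll 33 eligible patients on each of the two arms (66 total), in order to have 80% power", stratified on doubling time only.

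**Statistics after Amendment F.** Later in 5.4, the study "will enroll 31 eligible patients on each of the two arms (62 total"), for medians of 10.0 and 18.0 months. In addition, "patients will be stratified by combined androgen therapy status (progressed; beginning) as well as projected PSA doubling time". The accrual ceiling becomes 65. The calculation assumes an equal split between patients who have progressed on combined androgen therapy and those who have just begun it.

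**Analysis.** The primary test in 5.4 is a log-rank test with Kaplan-Meier plots. The plan does not say that it is stratified.

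**The concern.** The Amendment F paragraphs are part of the body of 5.4 and set out the operative design; they are not an amendment log. The document has since been amended at least as far as Amendment P, yet the sections that describe how patients are registered, randomised and treated were not brought into line.

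Three things follow. First, anyone setting up randomisation from 2.3, 3.1 or the Schema would stratify on doubling time only, and balance on combined androgen therapy status would be left to chance between two arms of about 31. Second, the arm size in 3.1 implies one patient more than the ceiling allows. Third, a population described as having had prior antiandrogen therapy is hard to square with a stratum of patients just beginning combined androgen therapy. Separately, the plan adds a stratification factor without saying whether the primary test uses it.

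**Working it through.** **1. The texts side by side**

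| Item | 2.3 | Schema | 3.1 | 5.4 after Amendment F |
|---|---|---|---|---|
| Factors named | doubling time | doubling time | doubling time | doubling time and combined androgen therapy status |
| Arm size | none given | none in the readable text | 33 | 31 |
| Total | none given | none in the readable text | 2 × 33 = 66 | 62, ceiling 65 |

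66 − 65 = 1 patient over the ceiling. Two binary factors give 2 × 2 = 4 strata instead of 2, or 62/4 = 15.5 patients per stratum on average.

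**2. Is 33 an alternative calculation or a leftover?** Inputs from 5.4: one-sided alpha 0.10, power 80%, 1:1 allocation, exponential times, accrual A and added follow-up F. I assume uniform accrual. The event probability per arm is 1 − [exp(−hF) − exp(−h(A+F))]/(hA), with h = ln 2/median. Required events are (1.2816 + 0.8416)² × 4/(ln HR)² by Schoenfeld, or (1.2816 + 0.8416)² × [(1+HR)/(1−HR)]² by Freedman.

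- Before Amendment F (7.6 vs 13.6 months, A=36, F=12): HR 1.79; event probabilities 0.902 and 0.752; 53.2 (Schoenfeld) or 56.3 (Freedman) events; 32.2 or 34.0 per arm. The stated 33 lies between them.
- After Amendment F (10.0 vs 18.0 months, A=60, F=24): HR 1.80; event probabilities 0.955 and 0.845; 52.2 or 55.2 events; 29.0 or 30.7 per arm. Lachin-Foulkes gives 30.9. The stated 31 is reproduced.

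Each size is right for its own inputs, so 33 in section 3.1 belongs to the superseded design.

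**3. Power under the Amendment F inputs**

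| Per arm | Expected events | Schoenfeld | Freedman |
|---|---|---|---|
| 31 | 55.8 | 82.0% | 80.3% |
| 33 | 59.4 | 83.7% | 82.1% |

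The difference is about 2 points.

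**4. Chance imbalance if status is not balanced.** With half the patients in each stratum and 31 per arm, the between-arm difference in the share progressed has SD √(2 × 0.5 × 0.5/31) = 0.127, or 12.7 points. The documents give no medians by stratum. As an assumption, take 7.6 months for the progressed stratum. A 50:50 exponential mixture with a 10-month median then needs 0.5·exp(−ln2·10/7.6) + 0.5·exp(−ln2·10/m) = 0.5, so m = 13.5 months and the between-stratum hazard ratio is 13.5/7.6 = 1.78. The approximate shift in the treatment log hazard ratio is the imbalance × ln(between-stratum hazard ratio):

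| Between-stratum HR (assumed) | One SD | Two SD |
|---|---|---|
| 1.00 | 0 | 0 |
| 1.25 | 0.03 | 0.06 |
| 1.50 | 0.05 | 0.10 |
| 1.78 | 0.07 | 0.15 |

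The target is ln 1.80 = 0.59 and the standard error at 55.8 events is √(4/55.8) = 0.27. In the last row, one SD is about 12% of the target and about 27% of the standard error.

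**5. Value of a stratified test.** I simulated the Amendment F design under the assumed medians (20,000 trials, 31 per arm, treatment HR 1.8 within each stratum, randomisation not stratified on status). Power was about 78% for the unstratified log-rank test and 79% for a log-rank test stratified on status. With randomisation also stratified on status, the figures were about 79% and 80%. Type I error was between 9.5% and 10.5% throughout.

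**The case against.** The strongest reply is that little harm has been shown, and much of it stands.

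- Section 2.3 calls doubling time a factor, not the only one. Randomisation is central, and the registration form comes from the Coordinating Center, which updates it as needed. Neither the form nor the eligibility checklist is in the documents, so a reader who infers that the second factor was never collected goes beyond the evidence. What stands is that 2.3, 3.1 and the Schema all omit a factor that 5.4 requires.
- A reader might infer that the trial has two live stopping sizes, 62 and 66. The documents do not support that: the later text in 5.4 is explicit about 62 and a ceiling of 65. The 33 is a stale label in 3.1. Section 2.3 gives no arm size, nor does the readable Schema text; the Schema figure is not shown.
- A reader might also infer that omitting the factor undermines the equal mix behind the 10 vs 18 month calculation. It does not. Stratification balances the arms; the mix depends on who enrols. That calculation uses one hazard per arm, and the plan specifies no stratified test.
- The 7.6 and 13.5 month medians are not document figures. Section 1.2.6 says the trial that gave 7.6 months included patients who had not progressed on earlier antiandrogens, and that similar proportions of patients with and without previous antiandrogen treatment had a sustained response. The strata may differ less, and the shift would shrink accordingly.
- Chance imbalance adds noise, not bias. The simulated gain from a stratified test is only 1 to 2 points.
- On population, criterion B in 2.1.1 does not require prior antiandrogen therapy, and 1.2.6 defends enrolment whether or not patients progressed on one. The sentence in 3.1 and the Schema is descriptive, but it still conflicts with a beginning stratum.

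**Conclusion.** The inconsistency is real and sits in current text. Following 2.3, 3.1 or the Schema would leave out a stratification factor that 5.4 requires, and filling both arms to the size shown in 3.1 would pass the ceiling by one patient. The document itself resolves the arm size in favour of 31, and the arithmetic agrees. The effect is modest: about 2 power points between 31 and 33 per arm, and a one-SD shift in the log hazard ratio from zero to about 0.07, depending on how far the strata differ. The upper figure rests on assumed medians of 7.6 and 13.5 months and an even split. The point should be corrected because the randomisation instructions do not match the plan and the correction is cheap. It does not invalidate the sample size calculation.

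**What to change.** 1. Add combined androgen therapy status (progressed; beginning) as a randomisation factor in 2.3, 3.1, the Schema and the registration checklist, or confirm that the checklist already has it.
2. Change n=33 to n=31 per arm in 3.1, consistent with 62 in total and the ceiling of 65.
3. Mark the pre-Amendment F design in 5.4 (33 per arm, 66 in total, doubling time only) as superseded.
4. Reconcile the description of the population in 3.1 and the Schema with 5.4 and 2.1.
5. State in 5.4 that the primary log-rank test is stratified by the randomisation factors. For patients randomised without combined androgen therapy status, derive it from baseline records. Section 5.4 counts 13 patients enrolled by Amendment F; any later patient randomised without the factor should be handled in the same way.

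Items 1 to 4 are text corrections and, at most, one extra field known at entry. Item 5 changes the analysis section and should be fixed before the outcome data are analysed by arm. It needs no extra patients or visits.
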